#### **8.1 Expected Toxicities**

##### **8.1.1 Adverse Events Lists**

###### **8.1.1.1 Adverse Event List(s) for Nivolumab**

Events that are listed as very common (experienced in  $\geq 10\%$  of patients) according to the current IB (Version 16 dated June 23, 2017) include the following: fatigue and diarrhea

Events that are listed as common (experienced in  $\geq 1\%$  to  $< 10\%$  of patients) include: hypothyroidism, hyperthyroidism, hyperglycemia, nausea, vomiting, chills, colitis, stomatitis, asthenia, gastritis,

abdominal pain, constipation, dry mouth, pyrexia, edema peripheral, infusion related reactions, increased lipase, increased amylase, increased aspartate aminotransferase, increase alanine aminotransferase, increased creatinine, increased thyroid stimulating hormone, hyponatremia, decreased appetite, back pain, myalgia, arthralgias, pain in extremity, headache, pruritis, dizziness, pneumonitis, dyspnea, cough, rash, vitiligo, dry skin, erythema, maculopapular rash

Events that are listed as uncommon  $\geq 0.001\%$  of patients to  $< 1\%$  include the following: musculoskeletal pain, arthritis, neck pain, musculoskeletal chest pain, bone pain, polyarthritis, peripheral neuropathy, peripheral sensory neuropathy, peripheral motor neuropathy, vasculitis, lung infiltration, tubulointerstitial nephritis, renal failure, acute kidney injury, hypertension, hypotension, alopecia, dermatitis acneiform, macular rash, urticaria, dermatitis, erythematous rash, generalized rash, papular rash, psoriasis, pustular rash, drug eruption, bronchitis, hypersensitivity, upper respiratory infections, edema, facial edema, peripheral swelling, localized edema, nephritis, autoimmune hepatitis, hepatitis, pancreatitis, uveitis, diabetes mellitus, thyroiditis, autoimmune hypophysitis, increased blood bilirubin, hypopituitarism, adrenal insufficiency, tachycardia, autoimmune colitis, atrial fibrillation, vertigo, dry eye, vision blurred, mucosal inflammation, generalized edema, respiratory failure, lung infiltration

Events that are listed as rare risk (experienced by  $\geq 0.00001\%$  to  $< 0.001\%$  of patients) include arrhythmias, Stevens Johnson Syndrome, dermatitis exfoliative, allergic dermatitis, rosacea, erythema multiforme, diabetic ketoacidosis, autoimmune hypothyroidism, iridocyclitis, periorbital edema, mouth ulceration, acute pancreatitis, acute hepatitis, sarcoidosis, anaphylactic reaction, myositis, musculoskeletal discomfort, osteoarthritis, pain in jaw, polymyalgia rheumatica, polymyositis, rhabdomyolysis, polyneuropathy, burning sensation, encephalitis, Guillain-Barre syndrome, myasthenia gravis, demyelination, autoimmune nephritis, organizing pneumonia, acute respiratory distress syndrome, vasculitis

Events that are listed as very rare (experienced by  $< 0.0001\%$ ) include ventricular arrhythmias, mucosal ulceration, demyelinating polyneuropathy, myasthenic syndrome, and toxic epidermal necrolysis

#### 8.1.1.2 Adverse Event List(s) for DC/MM Fusion Vaccines

Toxicities related to the vaccine are:

- Hematologic: Leukopenia
- Neurologic: Headache
- Gastrointestinal: Diarrhea, decrease appetite.
- Constitutional: Weakness chills and fever.
- Musculoskeletal: arthralgia and myalgia.
- Dermatologic: rash, itching, periorbital edema and local reaction in the site of infusion (swelling, pain, erythema and pruritus).
- Endocrine: elevated TSH.
- Other: ANA positivity

#### 8.1.1.3 Adverse Event List(s) for GM-CSF

Potential side effects of GM-CSF treatment include fever, chills, nausea, vomiting, diarrhea, fatigue, weakness, headache, decreased appetite, facial flushing, bone and muscle pain, local reaction at the site of injections, rashes, low blood pressure, shortness of breath and low blood counts. Rarely patients may develop blood clots, rapid or irregular heartbeats, feeling of faintness, kidney and liver problems, allergic reactions or fluid retention, including potential fluid retention in lungs or around the heart, and keratitis (inflammation of the cornea).

## 8.2 Adverse Event Characteristics

- **CTCAE term (AE description) and grade:** The descriptions and grading scales found in the revised NCI Common Terminology Criteria for Adverse Events (CTCAE) version 4.0 will be utilized for AE reporting. All appropriate treatment areas should have access to a copy of the CTCAE version 4.0. A copy of the CTCAE version 4.0 can be downloaded from the CTEP web site [http://ctep.cancer.gov/protocolDevelopment/electronic\\_applications/ctc.htm](http://ctep.cancer.gov/protocolDevelopment/electronic_applications/ctc.htm).
- **For expedited reporting purposes only:**
  - AEs for the agent(s) that are listed above should be reported only if the adverse event varies in nature, intensity or frequency from the expected toxicity information which is provided.
  - Other AEs for the protocol that do not require expedited reporting are outlined in the next section (Expedited Adverse Event Reporting) under the sub-heading of Protocol-Specific Expedited Adverse Event Reporting Exclusions.
- **Attribution of the AE:**
  - Definite – The AE is *clearly related* to the study treatment.
  - Probable – The AE is *likely related* to the study treatment.
  - Possible – The AE *may be related* to the study treatment.
  - Unlikely – The AE is *doubtfully related* to the study treatment.
  - Unrelated – The AE is *clearly NOT related* to the study treatment.

### 8.3 Adverse Event Reporting

8.3.1 In the event of an unanticipated problem or life-threatening complications treating investigators must immediately notify the Overall PI.

8.3.2 Investigators **must** report to the Overall PI any adverse event (AE) that occurs after the initial dose of study treatment, during treatment, or within 30 days of the last dose of treatment on the local institutional SAE form.

8.3.3 DF/HCC Adverse Event Reporting Guidelines

Investigative sites within DF/HCC will report AEs directly to the DFCI Office for Human Research Studies (OHRS) per the DFCI IRB reporting policy.

Attribution	DF/HCC Reportable Adverse Events(AEs)				
	Gr. 2 & 3 AE Expected	Gr. 2 & 3 AE Unexpected	Gr. 4 AE Expected	Gr. 4 AE Unexpected	Gr. 5 AE Expected or Unexpected
Unrelated Unlikely	Not required	Not required	5 calendar days #	5 calendar days	24 hours*
Possible Probable Definite	Not required	5 calendar days	5 calendar days #	5 calendar days	24 hours*
# If listed in protocol as expected and not requiring expedited reporting, event does not need to be reported.					
* For participants enrolled and actively participating in the study or for AEs occurring within 30 days of the last intervention, the AE should be reported within 1 business day of learning of the event.					

### **8.3.4 Protocol-Specific Adverse Event Reporting Exclusions**

AEs that occur prior to initiation of vaccine will not be captured or reported with the exception of AEs and SAEs that are related to tumor cell harvest and dendritic cell collection. Events that are thought to be related to tumor cell harvest or dendritic cell collection will be captured and reported as an SAE should it meet the DF/HCC as per DF/HCC guidelines.

AEs and SAEs will be captured and reported after initiation of vaccine will be captured and reported as per DF/HCC guidelines.

Laboratory abnormalities that are not clinically significant and are not related to study treatment will not be captured or reported.

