#### **1.3.2 Secondary Clinical Endpoints**

To determine the clinical response and safety of nivolumab and the DC/MM fusion vaccine in patients with relapsed disease. The percentage of patients achieving complete, very good partial and partial response will be quantified. Minimal residual disease (MRD) status will be determined. Progression free survival (PFS) will be assessed.

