### **5.12 Agent Administration**

#### **5.12.1 Nivolumab**

Patients will be treated with Nivolumab 240 mg on days 1 and 15 of a 28-day cycle. Nivolumab will be given every two weeks ( $\pm 3$  days). Patients may be dosed no less than 12 days from the previous dose of drug.

Nivolumab is to be administered as a 60-minute IV infusion (+/- 10 minutes), using a volumetric pump with a 0.2/1.2 micron in-line filter at the protocol-specified dose. The drug can be diluted with 0.9% normal saline for delivery but the total drug concentration of the solution cannot be below 1.0 mg/mL. It is not to be administered as an IV push or bolus injection.

Vital signs (BP, HR, Temp, RR, O2 sat) will be taken within 15 minutes prior to start of nivolumab infusion and within 15 minutes following completion of the infusion.

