#### **5.12.2 DC/MM Fusion Vaccine**

Patients will receive the DC/myeloma fusion vaccine/GM-CSF (vaccine) on day 1 of cycles 1, 2, and 3. Vaccine will be administered by subcutaneous injection with 100 ug GM-CSF given subcutaneously at the vaccine site on day of vaccination and daily for a total of 4 days of each cycle. The vaccine will be administered at least 1 hour following

Nivolumab infusion. On the first day of GM-CSF administration, 100 ug of GM-CSF subcutaneously will be administered subcutaneously. The patient will be trained to inject the remaining three GM-CSF injections (100ug dose once a day at the vaccination site) for self-administration subcutaneously at home.

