### **7. IDENTIFICATION OF TREATMENT LIMITING TOXICITIES**

Treatment limiting toxicities (TLT) will be defined as toxicity judged to be possibly or definitely related to the study treatment and meeting the following criteria:

- Grade 3 or higher non-hematologic toxicities that do not resolve within 14 days of onset;
  - Please note the following exceptions that necessitate immediate discontinuation of therapy:
    - Grade 4 creatinine elevation
    - Grade 3 or higher pulmonary toxicity
    - Grade 3 or higher ALT, AST or total bilirubin elevation
    - Grade 3 or higher adrenal insufficiency
    - Grade 3 or higher neurological adverse event
    - Grade 3 or higher myocarditis
- Grade 4 or higher clinically significant non-hematologic toxicities;
- Grade 4 or higher hematologic toxicities that do not resolve to grade 1 or baseline within 7 days of onset;
  - Please note that this excludes lymphopenia, as mentioned in section 5.9.3;
- Grade 4 or higher nivolumab infusion reactions.

Patients experiencing TLT will not receive further therapy

If 3 or more patients experience a TLT within the first 28 days of initiating therapy among the first 10 patients enrolled, then accrual will be suspended. TLTs will be defined per the above criteria with grades determined by CTCAE version 4.0 that are possibly, probably or definitely related to the study treatment. Patients will be monitored for the occurrence of TLTs during the first 28 days of treatment.

Once the 10th participant is enrolled, accrual will be paused until the 10th participant completes a full cycle of treatment (28 days) without experiencing any TLTs.

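### Section 8.3.4 starts adverse-event capture at the vaccine although nivolumab is given first, which contradicts the start point in Sections 8.3.2 and 8.7

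*Combined protocol and SAP*

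**What the plan says.** **The exclusion.** Section 8.3.4 states that "AEs that occur prior to initiation of vaccine will not be captured or reported". The one exception is for events "related to tumor cell harvest and dendritic cell collection"; events from nivolumab are not excepted. The next paragraph of 8.3.4 again starts capture after the vaccine, so the wording is not an isolated slip.

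**The order of agents.** Section 5.12.1 sets the infusion time at 60 minutes, with a tolerance of 10 either way. Section 5.12.2 then says of day 1: "The vaccine will be administered at least 1 hour following" the nivolumab infusion. In cycle 1, nivolumab is therefore the first study agent the patient receives.

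**The other start points.** Section 8.3.2 obliges investigators to report "any adverse event (AE) that occurs after the initial dose of study treatment". Section 8.7 requires all adverse events in routine submissions on the toxicity forms. Section 7 lists "Grade 4 or higher nivolumab infusion reactions" among the TLTs and counts TLTs over the first 28 days from the start of therapy, without reference to the vaccine.

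**The objective served.** Section 1.3.2 includes the aim "To determine the clinical response and safety of nivolumab and the DC/MM fusion vaccine in patients with relapsed disease".

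**The concern.** The plan gives two answers to the question of when adverse-event capture begins. Under 8.3.2 it begins with nivolumab; under 8.3.4 it begins with the vaccine. A reaction during the first nivolumab infusion, or in the hour or more before the vaccine, is reportable under one section and excluded under the other.

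This interval matters because an infusion reaction is the kind of event most naturally expected in it. Section 8.1.1.1 lists such reactions among the common nivolumab events, and Section 7 makes the most severe ones TLTs. If a site worked from 8.3.4 alone, reactions to the first dose could be missing from the safety tables. The omission could only make the combination look safer, because no rule in the plan would add events to compensate.

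**Working it through.** **1. The plan's own safety figure.** Section 14.1 gives the probability that enrollment continues, meaning 2 or fewer TLTs in 10 patients. For a true TLT rate p:

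P(continue) = (1−p)^10 + 10·p·(1−p)^9 + 45·p²·(1−p)^8

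At p = 0.25 this is 0.0563 + 0.1877 + 0.2816 = 0.5256, against 0.526 stated. At p = 0.10, 0.20, 0.30 and 0.40 it gives 0.9298, 0.6778, 0.3828 and 0.1673, against 0.930, 0.678, 0.383 and 0.167. The table is right. It assumes that every TLT is counted.

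**2. Length of the excluded interval on cycle 1 day 1.** Inputs are the infusion time (Section 5.12.1) and the minimum gap (Section 5.12.2).

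- Shortest permitted infusion: (60 − 10) + 60 = 110 minutes.
- Longest permitted infusion with the same minimum gap: (60 + 10) + 60 = 130 minutes.

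The gap has no upper limit, so both totals are minimums.

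**3. The rules applied to one event.** Take a reaction 30 minutes into the first infusion.

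- Section 8.3.4: before the vaccine and not from harvest or cell collection, so not captured.
- Section 8.3.2: after the initial dose has begun, so reportable.
- Section 8.7: an adverse event, so on the toxicity form.
- Section 7: within 28 days of starting therapy, so a TLT if grade 4 or higher.

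Section 8.3.4 cannot be applied to this event consistently with the other three.

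**4. A patient who might not reach the vaccine.** Section 7 gives no further therapy after a TLT. Section 6.1 allows vaccine alone when the toxicity is clearly due to nivolumab, and names infusion reactions as its example. These two passages need reconciling with each other. Whichever applies, the reaction itself precedes the vaccine and falls under the 8.3.4 exclusion.

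**5. How many events.** Section 8.1.1.1 places infusion-related reactions at 1% or more and below 10% of patients. For 25 patients that is 25 × 0.01 = 0.25 to just under 25 × 0.10 = 2.5 patients. The range covers all grades and all doses. The documents do not give the share at the first dose or the share at grade 4 or higher.

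**6. Illustration for the accrual rule.** Assume a true TLT rate of 25%, and assume that 1, 2 or 5 percentage points of it go uncounted. These shares are assumptions with no source in the documents. The formula in step 1, at the observed rate, gives:

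- observed 0.24: 0.556
- observed 0.23: 0.586
- observed 0.20: 0.678

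against 0.526 with full capture. This shows the direction and sensitivity of the rule and is not an estimate of what will happen.

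**7. A second source of uncertainty about the start date.** Section 14.1 describes a cycle of nivolumab during vaccine production, before any vaccination. Sections 1.1 and 5 describe standard of care therapy in that period, with nivolumab starting alongside the vaccine. If the Section 14.1 account were followed, the interval excluded by 8.3.4 would grow from about two hours to about one 28-day cycle.

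**The case against.** The best defense is that 8.3.4 was probably meant to keep adverse events of physician-chosen bridging therapy out of the database, with the vaccine used as shorthand for the start of immunotherapy. Its only exceptions are the study procedures that precede immunotherapy, which fits that purpose. The explanation is plausible, but the text says something else, and says it twice.

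Three stronger conclusions are tempting, and the documents do not support them.

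- **That 8.3.4 overrides 8.3.2.** Its title, as a protocol-specific exclusion, makes that reading available to a site. No section says that it prevails, and 8.3.2 and 8.7 are both worded as obligations.
- **That first-infusion reactions drop out of the TLT count.** Section 7 defines TLTs without reference to 8.3.4, names severe infusion reactions, and runs its window from the start of therapy. Section 8.3.1 requires immediate notice of life-threatening complications, and Section 6.2 describes a grade 4 infusion reaction as life threatening. Read as written, Section 7 counts the event.
- **That a patient who never receives the vaccine loses every adverse event.** The visit lists in Section 5 and the calendar in Section 11 schedule toxicity assessments that do not depend on vaccination, and Section 6.1 lets some of these patients go on to vaccine alone.

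It is also fair to say that 110 minutes is a duration and not a measure of bias, and that grade 4 reactions at a first infusion are likely to be few. Both points stand. They limit the likely size of the effect but leave the contradiction in place.

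**Conclusion.** The point holds as a contradiction between stated rules. Section 8.3.4, followed literally, excludes at least 110 minutes of first-dose nivolumab exposure in every treated patient, in conflict with Sections 8.3.2 and 8.7 and out of step with the TLT window in Section 7. This rests only on the order and timing of agents in Section 5.12.

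The consequence is conditional. If a site applies 8.3.4 in isolation, first-infusion reactions could be absent from the safety data, and the safety objective would be biased toward apparent safety. Loss of such events, including from the TLT count, is possible but not shown. The number affected cannot be derived: the all-grade, all-dose range of 0.25 to just under 2.5 patients in 25 is the most the documents allow, and the shifts in continuation probability above rest on assumed shares.

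It is still worth correcting before the trial relies on the rule, because the text is wrong as written, it bears on a stated objective, and the correction is nearly free.

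**What to change.** - In both places in Section 8.3.4, replace the reference to starting the vaccine with *first dose of any study agent (nivolumab or vaccine)*. This agrees with 8.3.2 and with the TLT window. It is safer than naming cycle 1 day 1, given the account in Section 14.1.
- Keep the exception for tumor harvest and dendritic cell collection. Adverse events of bridging therapy remain excluded.
- State that any patient who starts nivolumab belongs to the safety and TLT population, whether or not vaccine is given.
- Reconcile the pre-vaccine nivolumab cycle in Section 14.1 with Sections 1.1 and 5, so that the first dose of study treatment is a single, identifiable date.

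The cost is one wording change in 8.3.4, the added population statement, the reconciliation in Section 14.1, and slightly more adverse-event data entry on the first treatment day. No visit, procedure or treatment rule is added.

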### **8.4 Reporting to the Food and Drug Administration (FDA)**

The Overall PI, as study sponsor, will be responsible for all communications with the FDA. The Overall PI will report to the FDA, regardless of the site of occurrence, any serious adverse event that meets the FDA's criteria for expedited reporting following the reporting requirements and timelines set by the FDA.

### **8.5 Reporting to the Institutional Biosafety Committee (IBC)**

Participating investigators will register and report on research protocols involving biohazards (i.e., recombinant DNA or infectious agents) according to the reporting requirements set by their respective IBC.

### **8.6 Reporting to Hospital Risk Management**

Participating investigators will report to their local Risk Management office any participant safety reports, sentinel events or unanticipated problems that require reporting per institutional policy.

### **8.7 Routine Adverse Event Reporting**

All Adverse Events **must** be reported in routine study data submissions to the Overall PI on the toxicity case report forms. **AEs reported through expedited processes (e.g., reported to the IRB, FDA, etc.) must also be reported in routine study data submissions.**

## **9. PHARMACEUTICAL INFORMATION**

A list of the adverse events and potential risks associated with the investigational agent administered in this study can be found in Section 7.1.

### **9.1 Nivolumab**

#### **9.1.1 Description**

Nivolumab is a fully human monoclonal antibody (HuMAb; immunoglobulin G4 [IgG4]-S228P) that targets the PD-1 cell surface membrane receptor. Nivolumab inhibits the interaction of PD-1 with its ligands, PD-L1 and PD-L2, resulting in enhanced T-cell proliferation and interferon- gamma (IFN- $\gamma$ ) release in vitro.

#### **9.1.2 Form**

Nivolumab Injection, 100 mg/10 mL (10 mg/mL) is a clear to opalescent, colorless to pale yellow liquid, which may contain light (few) particulates. The drug product is a sterile, nonpyrogenic, single-use, isotonic

aqueous solution formulated at 10 mg/mL in sodium citrate, sodium chloride, mannitol, diethylenetriaminepentacetic acid (pentetic acid), and polysorbate 80, pH 6.0 and includes a 0.7 mL overfill to account for vial, needle, and syringe (VNS) holdup. It is supplied in 10-cc Type I flint glass vials, stoppered with butyl rubber stoppers and sealed with aluminum seals.

#### **9.1.3 Storage and Stability**

The product does not contain a preservative. Vials of nivolumab injection must be stored at 2-8°C (36°-46°F) and protected from light, freezing, and shaking.

After preparation, store the nivolumab infusion either: At room temperature for no more than 8 hours from the time of preparation. This includes room temperature storage of the infusion in the IV container and time for administration of the infusion or under refrigeration at 2°C to 8°C (36°F-46°F) for no more than 24 hours from the time of infusion preparation. Do not freeze. If a temperature excursion is noted, sites should follow institutional policies for notifying Bristol-Myers Squibb and assessing if the drug is still able to be used.

#### **9.1.4 Compatibility**

Do not co-administer other drugs through the same intravenous line. Flush the intravenous line at end of infusion. No incompatibilities between nivolumab and polyvinyl chloride (PVC), non-PVC/non DEHP (di(2-ethylhexyl)phthalate) IV components, or glass bottles have been observed.

#### **9.1.5 Handling**

Qualified personnel, familiar with procedures that minimize undue exposure to themselves and the environment, should undertake the preparation, handling, and safe disposal of the chemotherapeutic agent in a self-contained and protective environment.

#### **9.1.6 Availability**

Nivolumab for injection will be supplied free of charge by BMS.

#### **9.1.7 Preparation**

Visually inspect drug product solution for particulate matter and discoloration prior to administration. Nivolumab is a clear to opalescent, colorless to pale-yellow solution. Discard the vial if the solution is cloudy, is discolored, or contains extraneous particulate matter other than a few translucent-to-white, proteinaceous particles. Do not shake the vial.

Withdraw the required volume of nivolumab and transfer into an intravenous container.

Dilute nivolumab with either 0.9% Sodium Chloride Injection, USP or 5% Dextrose Injection, USP, to prepare an infusion with a final concentration greater than or equal to 0.35mg/ml .. Mix diluted solution by gentle inversion. Do not shake.

